In the R61 phase, we will examine the impact of SING on computational behavioral metrics of (Aim 1) Conditioned Hallucinations, (Aim 2) Social Reinforcement Learning, (Aim 3) Language Use, in 50 participants with voice hearing in the context of a psychotic illness. Following a screening visit to determine eligibility, these computerized tasks will be administered behaviorally, and an interview will elicit speech, prior to and following the full SING intervention (in 10 groups of 5 participants, each facilitated by a trained musical interventionist, during the first two years of the project). If SING meaningfully alters these computational task parameters (decision criteria outlined below), we will proceed to the R33 phase, wherein we will recruit a further 200 voice hearing participants with similar diagnoses. These participants will complete the same

tasks deemed mechanistically relevant in the R61 phase, prior to and following randomization to four different conditions (facilitated by an interventionist musician) that will deconstruct the possible active ingredients of SING along two dimensions: Activity and Ownership: (a) SING (n=50, Activity + and Ownership +), participants produce and perform their own song; (b) Karaoke (n=50, Activity + and Ownership -), participants perform karaoke, singing along to others music; (c) Pop Music (n=50, Activity – and Ownership -), participants will listen to popular music chosen by the music interventionists; and (d) Curated Playlists (n=50, Activity -, Ownership +), participants will curate playlists of popular music and listen to them together. This deconstruction will provide insights into the predictive processing framework, as applied to hallucinations and music, specifically, whether changes at higher, a-modal, hierarchical levels, particularly sense of self and active inference, influence precision weighted perceptual and social inferences more so than inactive experiences or experiences that do not engage sense of self.

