R61 Statistical Power: Aims 1-3: Since all participants will perform all studies in Aims 1-3 (Conditioned Hallucinations, Social Learning and Linguistic Markers), we powered our study based on our own preliminary data. Estimated effects for our proposed study of the impact of SING on conditioned hallucinations model parameters are based upon our own data in **Figure 2**. If SING can curtail these group differences – i.e. decrease hallucinating patient responses to the level of non-hallucinating controls, then we would predict the true difference in HGF model parameters pre- versus post-SING would be 0.01 arbitrary units and the within-patient standard deviation of the parameter estimates would be 0.02. We will analyze the model parameter specific to each Aim using paired sample's t-tests, leveraging the added power of within-participant designs. We estimate we will need at least 31 participants to have 80% power to detect a treatment difference at a two-sided 0.05 significance level⁵⁴. We budgeted for 50 unique participants to allow for participant drop-out and the detection of smaller effects of SING on conditioned hallucination behavior, social learning and language use.

Go/No Go Decision: We powered the R61 phase in order to detect complete resolution of conditioned hallucination metrics to the level of non-hallucinating control participants. But we propose a much larger sample of participants in order to be powered to detect smaller changes in conditioned hallucination metrics, social learning and language use. Given standard pharmacotherapies for hallucinations are associated with residual symptoms in 30-50% of participants⁵⁵, it would seem an unfairly high bar to demand complete normalization of a candidate behavioral metric in order for an effect on that metric to be meaningful and solicitous of follow-up investigation. In the clinical trials literature, Jacobson and Truax⁵⁶ determining clinical significance is often used. It is defined as two standard deviations or greater change in the direction of symptomatic improvement following treatment. We propose to adopt this standard for each metric examined in each of Aims 1-3. **Conditioned Hallucination parameters, social learning rates or use of personal pronouns, biological words or negative emotional words change by two standard deviations or more from baseline pre-intervention, then those metrics will proceed to our R33 study. If no metrics meet that standard, we will not proceed with the R33.**

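### The R61 minimum of 31 participants falls short of 80% power for the paired t-test on the inputs as printed (34 are needed), and the plan does not say which standard deviation 0.02 is

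*Combined protocol and SAP*

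**What the plan says.** The R61 Statistical Power paragraph in Section I, item 13 gives all the planning inputs. The assumed effect is that "the true difference in HGF model parameters pre- versus post-SING would be 0.01 arbitrary units", and the assumed spread is that "the within-patient standard deviation of the parameter estimates would be 0.02". The analysis is named: "We will analyze the model parameter specific to each Aim using paired" t-tests. From these the plan concludes: "We estimate we will need at least 31 participants to have 80% power to detect a treatment difference at a two-sided 0.05 significance level". A biostatistics textbook is cited, but no formula, pre-post correlation, SD of the difference or drop-out rate is given.

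The paragraph then adds headroom: "We budgeted for 50 unique participants to allow for participant drop-out and the detection of smaller effects of SING". The Go/No Go Decision paragraph relies on the same calculation: "We powered the R61 phase in order to detect complete resolution of conditioned hallucination metrics", followed by "But we propose a much larger sample of participants in order to be powered to detect smaller changes in conditioned hallucination metrics".

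The R33 Power to Detect Effects paragraph repeats the 0.01, the 0.02 with the same label, and the 31.

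**The concern.** There are two linked problems.

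- **The number does not match the test.** A minimum sample size stated for 80% power should reach 80% under the analysis that the plan names. On the printed inputs, 31 does not.
- **The SD is not identified.** A paired t-test is sized on the SD of the pre-post difference. The plan's label speaks of parameter estimates within a patient, which can be read in more than one way, and the required number depends strongly on which reading is meant.

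This is the only sample-size justification for R61. If 0.02 turned out to be the SD of a single estimate, the statements that 50 leaves room for drop-out and smaller effects, and that the phase is powered for full normalisation, would no longer hold as written.

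**Working it through.** **Inputs**, all from the R61 Statistical Power paragraph: change 0.01; SD 0.02; two-sided alpha 0.05; power 80%; paired t-test; 50 budgeted.

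**1. Reproducing the stated 31.** Take 0.02 as the SD of the difference, so d = 0.01/0.02 = 0.5. The paired normal approximation is

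n = (z0.975 + z0.80)² / d² = (1.960 + 0.842)² × 4 = 7.849 × 4 = 31.4.

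Rounded down this is 31. Rounded up, as a minimum should be, it is 32. Under this approximation, power is 79.5% at 31 and 80.7% at 32.

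**2. The named test.** Power of the two-sided paired t-test (non-central t, n − 1 degrees of freedom, non-centrality 0.5 × √n):

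| Completers | Power |
|---|---|
| 31 | 76.8% |
| 32 | 78.2% |
| 33 | 79.5% |
| 34 | 80.8% |
| 50 | 93.4% |

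The minimum is 34. With 50 completers the effect detectable with 80% power is d = 0.404, a change of 0.404 × 0.02 = 0.0081. These figures treat participants as independent, although SING is delivered "in 10 groups of 5 participants, each facilitated by a trained musical interventionist".

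**3. Margin in the budget.** From 50, 34 completers remain after 1 − 34/50 = 32% drop-out. By the stated 31 the margin is 1 − 31/50 = 38%.

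**4. What else 0.02 could be.**

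- *Per-visit SD with pre-post correlation ρ.* SD of the difference = 0.02 × √(2(1 − ρ)). At ρ = 0.5 this is 0.02, so the result is again 31.4 by approximation and 34 by t-test. This reading reproduces the plan's figure as well as step 1 does. The plan gives no ρ; over an assumed range the t-test needs 65 at ρ = 0, 50 at 0.25, 34 at 0.5 and 18 at 0.75.
- *SD of a single within-patient estimate* (assuming independent errors and the same true change in every patient). SD of the difference = 0.02 × √2 = 0.0283, so d = 0.354. The approximation gives 7.849 × 8 = 62.8 and the t-test needs 65. Power is 47.8% at 31 and 68.8% at 50. The change detectable with 50 completers is 0.404 × 0.0283 = 0.0114. This reading does not reproduce 31.

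**5. Could rounding of the inputs explain 31?** Yes. The t-test gives n = 31 for a change of 0.0100 with an SD of 0.0190 to 0.0192, or for a change of 0.0105 with an SD of 0.0200. Each value rounds to what is printed.

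**The case against.** The strongest reply is that 31 is a rounded planning estimate and that nothing hangs on it. The budget is 50, which gives 93% power on the SD-of-difference reading and tolerates 32% drop-out against the t-test minimum. The go/no-go rule uses a change of two standard deviations from baseline, not this t-test. All of that stands, and it is why the point is minor. It does not make the stated minimum right for the named test.

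A second reply is that the inputs are printed to one significant figure, so a gap of 3 lies within what rounding can produce. That also stands. The finding is therefore limited to the inputs as printed, and giving the unrounded inputs would be an acceptable answer.

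Three stronger readings are tempting, and the documents do not support them:

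- *That the investigators used the normal approximation and rounded the wrong way.* The match at 31.4 suggests it, but no formula is shown.
- *That R61 is underpowered and needs 65.* This follows only if 0.02 is the SD of a single estimate, and that reading would have produced about 63 rather than 31.
- *That the same paired-test figures correct R33.* That paragraph describes a 2×2 analysis of variance, so only the SD label carries over.

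**Conclusion.** The point holds as a minor one. On the printed inputs, with 0.02 as the SD of the pre-post difference (or a per-visit SD with correlation 0.5), the stated minimum is 3 too low for the paired t-test: 76.8% power at 31, against 34 participants for 80%. Confidence in that arithmetic is high. How 31 was obtained is not established.

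The label on 0.02 is the part that needs an answer from the investigators, because the documents do not settle it. The printed 31 favours an SD of the difference of 0.02, stated directly or implied through the correlation. Under that reading the drop-out and smaller-effects sentences remain true. Only under the single-estimate reading would the power claims at 50 fail (69%).

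**What to change.** The changes are to protocol wording only, with no change to enrolment.

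1. In R61 Statistical Power, state which SD 0.02 is and which data it came from. The paragraph cites Figure 2 for its effect estimates and describes what it takes from that figure as group differences. A comparison between groups does not by itself supply a pre-post SD, so the source needs naming. If a per-visit SD was used, give the assumed pre-post correlation.
2. If the SD of the difference is 0.02, directly or by implication, replace 31 with 34 and say that it is for the paired t-test, or print the unrounded inputs that yield 31. Where 0.02 is kept as printed, add that 50 completers, treated as independent, give 93% power and can detect a change of 0.0081 with 80% power. Keep the drop-out and smaller-effects sentences.
3. If 0.02 is the SD of a single within-patient estimate, restate the minimum as 65 and the power with 50 completers as 69%. Then revise the sentence on drop-out and smaller effects, and the two Go/No Go sentences on powering for full normalisation and on the larger sample.
4. Clarify the same SD label in R33 Power to Detect Effects, without copying the paired-test figures there.

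The cost is one check by the investigators of where 0.02 came from, and a few lines of text.

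### The R61 Go rule does not define its SD or its unit; for the conditioned hallucination parameter, read as a group mean with the plan's SD of 0.02, its bar is four times complete normalization

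*Combined protocol and SAP*

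**What the plan says.** Section I, item 4 (Research Plan) makes the second phase conditional: "If SING meaningfully alters these computational task parameters (decision criteria outlined below), we will proceed to the R33 phase". The criteria themselves are in item 13.

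- **R61 Statistical Power.** Bringing hallucinating patients to the level of non-hallucinating controls is taken as a true pre-post difference that "would be 0.01 arbitrary units and the within-patient standard deviation of the parameter estimates would be 0.02". The analysis is stated as: "We will analyze the model parameter specific to each Aim using paired sample's t-tests". The sample size is at least 31 for 80% power at two-sided 0.05. Fifty are budgeted, to cover drop-out and to detect smaller effects.
- **Go/No Go Decision.** The phase was powered for complete resolution of the CH metrics. The text continues: "But we propose a much larger sample of participants in order to be powered to detect smaller changes in conditioned hallucination metrics". Because standard drug treatment leaves residual symptoms, "it would seem an unfairly high bar to demand complete normalization of a candidate behavioral metric". The plan then adopts a published clinical-significance standard: "It is defined as two standard deviations or greater change in the direction of symptomatic improvement following treatment". The operative rule is that metrics which "change by two standard deviations or more from baseline pre-intervention, then those metrics will proceed to our R33 study". It closes: "If no metrics meet that standard, we will not proceed with the R33".

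The only other detail on the rule is in item 4, Quantitative Analysis, which makes three word categories one step of the decision. No section gives the SD or the unit.

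**The concern.** A two-SD rule cannot be applied until two things are fixed. One is the SD: of the paired change, of the baseline values, or of controls. The other is the unit: the group mean, or each participant, in which case a required share is needed. The wording says what the change is measured from, but neither of these.

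The rule also conflicts with its own paragraph on one natural reading. The paragraph sets out to ask for less than complete normalization. If the rule applies to the mean change, with the only SD the plan prints, it asks for much more.

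This rule decides which metrics enter a 200-participant phase. If its terms are settled after the R61 data are seen, the choice of SD, unit and share can decide the result. On the group-mean reading with SD 0.02, enlarging the sample to detect smaller changes does not help the CH parameter reach Go, although drop-out remains a valid reason for the larger number.

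**Working it through.** **Inputs** (item 13): change at full normalization 0.01; SD 0.02; two-sided 0.05; 80% power; N = 31; 50 budgeted. The pre-post correlation r and the ratio k of post to pre SD are not given and are assumed below.

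**1. The plan's own N.** N = (1.96 + 0.8416)² × (0.02/0.01)² = 31.4, which agrees with 31 to within rounding. If 0.02 were a per-visit SD with independent visits, N would be 62.8. So 0.02 acts as the SD of the paired change, and full normalization is 0.01/0.02 = 0.5 SD.

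**2. Group mean, SD 0.02.** Bar = 2 × 0.02 = 0.04, or 4 × 0.01. For 2 × SD to be no more than 0.01, the SD must be 0.005 or less, a quarter of 0.02. With 50 completers the standard error is 0.02/√50 = 0.00283. At full normalization the bar lies (0.04 − 0.01)/0.00283 = 10.6 standard errors above the true mean, so Go is effectively nil. The planned paired t-test (noncentral t) has 93% power at 0.01 with 50 completers and 77% with 31.

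**3. Group mean, baseline SD.** Baseline SD = 0.02/√(1 + k² − 2rk).
- Equal SDs (k = 1): the bar is 2.8, 4.0, 5.2 and 6.3 times normalization at r = 0, 0.5, 0.7 and 0.8. Go is effectively nil throughout.
- Larger post SD, r = 0: 1.8 times at k = 2 (Go 0.3%) and 1.3 times at k = 3 (Go 17%).
- A control-group SD cannot be assessed from the text.

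**4. Per participant, SD 0.02.** A participant passes with probability P(Z > (0.04 − 0.01)/0.02) = P(Z > 1.5) = 6.7% at full normalization, and P(Z > 2) = 2.3% with no effect. Binomial, n = 50:

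| Required share | Go at full normalization | Go with no effect |
|---|---|---|
| any 1 of 50 | 97% | 68% |
| 3 of 50 | 66% | 11% |
| 5 of 50 | 24% | 0.6% |
| 10 of 50 | 0.2% | nil |

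**5. Per participant, baseline SD, any one of 50, full normalization, k = 1.**

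| r | 0 | 0.5 | 0.7 | 0.8 | 0.9 |
|---|---|---|---|---|---|
| Chance of Go | over 99.9% | 97% | 61% | 18% | 0.2% |

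Item 4 (R61 Aim 1) calls the parameters stable over time, but on six people, so it does not fix r.

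**The case against.** The best defence is that the rule never speaks of a mean. It borrows a clinical-significance standard, which fits a judgement on individuals, and on that reading there is no fourfold conflict. The cited source may also define the SD and the unit. The first part stands: the conflict belongs to the group-mean reading, and the Go paragraph names no test. But the per-participant reading has its own gap, the missing share, and step 4 of the working shows that this alone moves Go from near certain to near zero. What the source may contain is not in the plan, and the plan's paraphrase gives only size and direction.

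Other points carry some weight. The figures of 0.01 and 0.02 come from a figure that is not shown, so the check rests on the values printed in the text. Two SDs could be less than normalization if SD were used loosely for the standard error (2 × 0.00283 = 0.0057), but the plan does not say so. The direction of change is not in dispute, since the preceding sentence gives it. The sponsor chose a size-of-change criterion, and replacing it outright with a significance test would be partly a matter of preference.

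A reader might infer that R33 cannot go ahead under this rule. The documents do not support that. One passing metric is enough, and no effect or SD is given for social learning or word use.

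**Conclusion.** The point holds in limited form. The plan fixes neither the SD nor the unit of its Go rule. For the CH parameter, read as a group mean with SD 0.02, the bar is four times complete normalization and contradicts the stated intent. This is a faulty decision threshold as well as missing detail, and it needs correcting before R61 data are examined.

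The fourfold figure rests on 0.01 and 0.02 as printed, on 0.02 being the SD of paired change (which the stated N supports), and on the group-mean reading. The chances of Go assume normally distributed, independent changes and 50 completers. The baseline-SD results also rest on assumed r and k. Nothing is shown for the other metrics or for the phase as a whole.

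**What to change.** Before R61 data are examined, revise the Go/No Go paragraph as follows.

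- State the SD, the unit and, if the rule is per participant, the required share.
- Fix a named list of Go metrics. Name the CH parameter or parameters, and reconcile personal pronouns (item 13) with the I category (item 4, Quantitative Analysis).
- Set the bar below complete normalization, as the paragraph intends. For CH on a group-mean rule, that is a mean change below 0.01 (0.5 SD of change).
- State that Go refers to total pre-post change, because R61 has no control arm.

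One option that matches the power basis is a mean change in the predicted direction, significant on the planned paired test with false discovery rate (FDR) control across the list. A minimum change can be kept alongside it. For CH it adds to the unadjusted test only above t × 0.02/√n: about 0.0057 with 50 completers or 0.0073 with 31. If a test is used, fix in advance how it handles the 10 SING groups, the medication covariate (item 8) and the possible weighting by facilitator notes (item 4, SING Intervention).

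**Cost.** Wording and slightly more analysis. For the test option:

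- **False Go.** Against the group-mean reading it rises from near zero to 2.5% per metric before FDR. With FDR over five independent null metrics (five is an assumed count), simulation gives about 2.6% for any Go.
- **Drift.** An assumed non-SING drift of 0.002 to 0.004 would raise false Go for CH to 10% to 28% before FDR, with 50 completers.
- **Groups.** A t-test on the 10 group means lowers Go at full normalization from 93% to 88% with no clustering, and to 65% at an assumed intraclass correlation of 0.20, before FDR.

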A total of 250 (50 in R61, 200 in R33) voice hearing patients (aged 18-65 years) meeting diagnostic criteria for DSM-V psychotic disorder, hearing voices at least once a day, and PANSS P3 (Hallucinations item) greater than 3, will be recruited from the local community via advertisement, from databases of ongoing Clinical Neuroscience Research Unit projects, community outpatient facility contacts and among the patients being recruited under [name] existing STEP clinic protocol, patients attending the Psychosis Clinic at the Connecticut Mental Health Center, Program for Recovery and Community Health, and the Connecticut Hearing Voices Network. Prior to study participation all patients will be evaluated for i) protocol eligibility; ii) interaction with the study team to determine participant's probability of completing the study; and iii) ability to cooperate with protocol procedures. The flow of all participants will be reviewed at weekly research meetings in consultation with the study team. Exclusion Criteria: i) DSM-IV substance abuse or dependence (past six months); ii) clinically significant medical conditions, head injury with neurological symptoms or unconsciousness; iii) mental retardation (IQ<70); iv) Non-English speaking; v) no less than 2 weeks of stable doses of psychotropic medications (to avoid transient effects of medication regiment change; medication type and dose will be carefully recorded and used as a covariate in all analyses); vi) Co-morbid mood or anxiety diagnosis; viii) clinically/behaviorally unstable and unable to cooperate with SING procedures. ix) Unstable medical condition based on medical history, physical examination and routine laboratory work-up, including a urine drug screen for illicit substance use (results will remain confidential, they will not be retained, and they will only be used for eligibility determination).

9. **Eligibility:** *How will eligibility be determined, and by whom?*

Eligibility will be determined initially by a telephone pre-screen and then confirmed with an in-person interview, by [name] and his team.

10. **Risks:** *Describe the reasonably foreseeable risks, including risks to subject privacy, discomforts, or inconveniences associated with subjects participating in the research.*

The risks from this study include 1) emotional distress, and 2) confidentiality.

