		ACTIVE	
		-	+
OWNERSHIP	-	Listening (pop music) n=50	Karaoke (no recording) n=50
	+	Listening (curated playlists) n=50	SING (producing, performing) n=50

Figure 6. R33 Design

R33 Phase: Should we demonstrate a meaningful impact of SING on computational metrics of behavior, we will proceed to use those metrics in the R33 phase where we aim to deconstruct the active ingredients of SING along two key dimensions, Activity (whether engagement with the group is active or passive) and Ownership (creating some novel musical product, or not). Following screening, once participants have been deemed eligible, their behavior on the selected behavioral metrics will be assayed and they will be randomized to an intervention group. Performance on our computational metrics will be balanced across intervention groups prior to commencement of the four interventions (total n=200, n=50 per intervention, 10 groups of 5 participants per intervention):

- (1) **Passive Listening without Ownership** (Activity - / Ownership -, n=50). The group will meet on four occasions, once a week for two hours. The trained facilitator, having procured a playlist of popular music, will spend 15 minutes introducing the session, reminding participants not to sing along and to just sit quietly listening to the music. Next, the facilitator will play music from the playlist through a high-quality speaker at 60-75 decibels for 90 minutes. In the final 15 minutes, the facilitator will summarize the session and dismiss the participants, sharing follow-up music opportunities at the end of the fourth and final session.

- (2) **Passive Listening with Ownership** (Activity - / Ownership +, n=50). The trained facilitator will provide a computer and speaker with the ability to stream songs through many media outlets (i.e., Spotify, YouTube, Google). In the first fifteen minutes, the facilitator will introduce the session, participants are reminded not to sing along and to just sit quietly listening to the music. Next the participants will choose songs that they would like to hear. The list can be edited at any point. For the next 90 mins, the playlist will be played through a high-quality speaker at 60-75 decibels. In the final 15 minutes, the group will be concluded, and the participants will be dismissed. If it is the final session, they will be offered follow-up information about the musical opportunities.

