R33 Power to Detect Effects. Since all participants will perform all tasks; Conditioned Hallucinations, Social Learning and Linguistic Markers, we powered the R33 based on our own preliminary data (on the understanding that any and all of the tasks from the three R61 aims may or may not progress to the R33). Estimated effects for our proposed study of the impact of SING on conditioned hallucinations model parameters are based upon our own data in **Figure 2**. If SING can curtail these group differences – i.e. decrease hallucinating patient responses to the level of non-hallucinating controls, then we would predict the true difference in HGF model parameters pre- versus post-SING would be 0.01 arbitrary units and the within-patient standard deviation of the parameter estimates would be 0.02. We will analyze the model parameter specific to each of the four interventions in a 2x2 design (Activity vs Ownership) using Analysis of Variance, leveraging the added power of within-participants designs. We estimate we will need at least 31 participants to have 80% power to detect a treatment difference at a two-sided 0.05 significance level⁵⁴. We budgeted for 50 unique participants per group to allow for participant drop-out and the detection of smaller effects of SING on conditioned hallucination behavior, social learning and language use.

Robustness and reproducibility (both phases). We have built in a replication study of the effects of SING on conditioned hallucinations, social learning and language use across our R61 and R33 studies (should those metrics satisfy our Go/No-Go criteria). We have chosen to focus on metrics with face and construct validity for psychosis, whose implication in the mechanisms of psychosis have been conceptually replicated across labs in different cities⁵⁷ and countries⁵⁸. Our tasks, analysis code, and data will be made freely available via Yale's ModelDB site. We will optimize and manualize the SING and control interventions in order to prosecute the R61 and R33. Those manuals will be available open access also.

SECTION II: RESEARCH INVOLVING DRUGS, BIOLOGICS, RADIOTRACERS, PLACEBOS AND DEVICES

If this section (or one of its parts, A or B) is not applicable, check off N/A and delete the rest of the section.

- A. RADIOTRACERS N/A
- B. DRUGS/BIOLOGICS N/A
- C. DEVICES N/A

SECTION III: RECRUITMENT/CONSENT AND ASSENT PROCEDURES

1. Targeted Enrollment: *Give the number of subjects.*

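### R33 balances its arms on the baseline metrics, but its 2x2 ANOVA names no baseline covariate, balancing factor or group term, so it gives up power that the collected data could supply

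*Combined protocol and SAP*

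**What the plan says.** All the places are in Section I of the combined protocol and SAP.

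- **Item 13, R33 Phase.** Eligible participants are measured on the selected metrics and then randomised to four arms of 50, each made up of ten groups of five. The plan adds: "Performance on our computational metrics will be balanced across intervention groups prior to commencement of the four interventions". It does not say how the balance will be achieved.
- **Item 13, R33 Power to Detect Effects.** The metrics will be analysed "in a 2x2 design (Activity vs Ownership) using Analysis of Variance, leveraging the added power of within-participants designs". No baseline covariate, balancing factor or group term is named.
- **Item 13, R61 Statistical Power.** The R61 comparison is made "using paired sample's t-tests, leveraging the added power of within-participant designs".
- **Item 8, Inclusion/Exclusion Criteria.** Within the criterion on stable medication, the plan says that "medication type and dose will be carefully recorded and used as a covariate in all analyses".
- **Sample size, both phases.** The plan asks for "at least 31 participants to have 80% power to detect a treatment difference at a two-sided 0.05 significance level". The effect behind this figure is a 0.01-unit shift in the model parameter from before to after SING. For the spread, it supposes that the "within-patient standard deviation of the parameter estimates would be 0.02".

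**The concern.** R33 measures each metric before randomisation and uses it to form the arms, but the analysis then uses it only as the starting point of a change score. A pre-post ANOVA of this kind tests Activity and Ownership through change, which fixes the baseline slope at 1 instead of estimating it. Unless the pre-post correlation is close to 1, variation predictable from baseline stays in the residual and power is lost. R33 has little to spare on two-arm contrasts and on the interaction.

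Two matters of specification go with this. Participants share four sessions in groups of five, and the analysis has no term for that. Item 8 promises a medication covariate everywhere, but item 13 names only paired t-tests and ANOVA and does not say how type and dose would be coded. Unless the model is written down, these choices could be made after the data are seen.

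**Working it through.** **Inputs from the documents.** Difference 0.01, SD 0.02, two-sided 5%, 80% power, 50 per arm, groups of five.

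**Assumptions.** Pre-post correlation ρ of 0.3 to 0.9, since none is given; equal variance before and after; and, until step 5, independent participants and no dropout.

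**1. The plan's own figure.** n = (1.960 + 0.842)² × (0.02/0.01)² = 31.4. The stated 31 is therefore a one-sample calculation on pre-post change, and 0.02 has to be read as the SD of that change. It is not a between-arm size: a 0.01 difference in change between two arms needs 2 × 7.849 × 4 = 62.8, or 63 per arm. In the plan 0.01 is a within-arm change, so using it below as a between-arm difference or an interaction is an assumption.

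**2. Variance.** With per-occasion variance σ², change has variance 2σ²(1−ρ). After baseline adjustment the residual variance is σ²(1−ρ²). The ratio is (1+ρ)/2.

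**3. Power.** The unadjusted standard errors are:

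- two arms, 50 v 50: √(2 × 0.02²/50) = 0.0040
- interaction (difference of differences): √(4 × 0.02²/50) = 0.00566
- main effect, 100 v 100: √(2 × 0.02²/100) = 0.00283

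Power is Φ(0.01/SE − 1.96), with each SE multiplied by √ratio for the adjusted analysis.

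| | Variance ratio | Excess SE without adjustment | Two arms | Interaction | Main effect |
|---|---|---|---|---|---|
| Change ANOVA | 1 | – | 70.5% | 42% | 94% |
| Adjusted, ρ = 0.3 | 0.65 | 24% | 87% | 59% | 99% |
| Adjusted, ρ = 0.5 | 0.75 | 15% | 82% | 53% | 98% |
| Adjusted, ρ = 0.7 | 0.85 | 8% | 77% | 48% | 97% |
| Adjusted, ρ = 0.9 | 0.95 | 3% | 73% | 44% | 95% |

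If SING alone changes, by 0.01, each main effect is only 0.005, and its power matches the interaction column.

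**4. Type I error of the change ANOVA, independent participants.** If balancing removes baseline differences between arms almost entirely, the true SE is √ratio times the model SE. The error is then 2 × [1 − Φ(1.96/√ratio)] = 1.5%, 2.4%, 3.4% and 4.4% for ρ = 0.3, 0.5, 0.7 and 0.9. Simulation with 200 baselines sorted and allocated in blocks of four gave 1.8%, 2.2%, 3.8% and 4.7%. With ordinary randomisation and no forced balance, the error is about 5%.

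**5. Clustering.** The documents give no intraclass correlation (ICC). Assuming 0.05 or 0.10, the design effect is 1 + 4 × ICC = 1.2 or 1.4. Under the same tight balancing, simulated type I error was:

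| | Change ANOVA, ICC 0.05 | Change ANOVA, ICC 0.10 | ANCOVA without group term, ICC 0.05 | ANCOVA without group term, ICC 0.10 |
|---|---|---|---|---|
| ρ = 0.5 | 4.6% | 6.0% | 7.8% | 10.5% |
| ρ = 0.7 | 5.9% | 8.5% | 7.8% | 11.4% |
| ρ = 0.9 | 6.5% | 8.7% | 7.2% | 9.9% |

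The two influences cancel where (1+ρ)/2 × design effect = 1, which is ρ = 0.67 at ICC 0.05 and ρ = 0.43 at ICC 0.10. Clustering also lowers the adjusted powers in step 3. At ρ = 0.5 and ICC 0.05 the variance factor is 0.75 × 1.2 = 0.90, and two-arm power is Φ(2.5/√0.90 − 1.96) = 75%, not 82%.

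**6. Medication covariate.** If it explained 2% to 10% of the variance of change (assumed), two-arm power would move from 70.5% to between 71% and 75%.

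**The case against.** The best defence is that nothing planned here is invalid. The R33 analysis is described as within-participant, so the pre-intervention value already enters through change, and under ordinary randomisation that analysis holds 5%. The protocol also calls the conditioned-hallucination parameters stable over time. If that means a correlation near 0.9, the loss is about 3% of the standard error. A full 0.01 main effect has 94% power as planned. All of this stands, except that the stability rests on six people (one of them hallucinating), with no correlation reported, so it does not establish 0.9 in treated voice-hearers.

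Two stronger readings are tempting, and the documents do not support them.

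- **A reader might infer that the R33 intervals are too wide and the tests run well below 5%.** That needs tight balancing and independent participants. The method of balancing is not described, more than one metric may have to be balanced, and working in groups of five pushes the error upwards. Nor is ANCOVA alone a safe remedy: without a group term it exceeded 7% in every clustered setting simulated.
- **A reader might infer that the named tests cannot carry the medication covariate.** This is true only of the R61 paired t-test. The R33 ANOVA becomes an ANCOVA once a covariate is added, and item 8 already commits to one, so for R33 the texts are under-specified and not opposed. A stable additive medication effect also cancels in change, so this covariate may add little power.

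**Conclusion.** The point holds as one of efficiency and specification, and the change is worth making. R33 balances on baseline but does not adjust for it, and recovering the lost precision needs no new data. The gain is useful for two-arm contrasts and the interaction if the pre-post correlation is moderate, small if it is near 0.9, and minor for a full 0.01 main effect. All the power figures rest on an assumed correlation, an SD of change of 0.02, a between-arm reading of 0.01, no dropout and, except where stated, no clustering. The net direction of the type I error is not established. Separately, and whatever the correlation, the R61 t-test and the covariate promise in item 8 cannot both be followed as written.

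**What to change.** - **R33 Power to Detect Effects.** Replace the ANOVA with a mixed-model ANCOVA: post-intervention metric on Activity, Ownership and their interaction, with the baseline value of that metric, any balancing factors, the medication covariates (both type and dose, with their coding fixed in advance) and a random effect for intervention group.
- **R33 Phase.** State how balance will be achieved and on which metrics, so that the balancing factors in the model are defined.
- **R61 Statistical Power and item 8.** Reconcile the two. Either estimate mean change as the intercept of a regression of change on centred medication covariates, which leaves the estimate equal to the plain mean change, or limit the wording of item 8 to the analyses that will carry the covariate.

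The cost is analysis wording plus a few degrees of freedom. Baseline metrics are already measured before randomisation, medication is already to be recorded, and group membership is known.
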